The melatonin will be administered rectally in a fluid, followed by plasma samples over the following 24 hours. The melatonin formulation applied for rectal administration will be a 2.5 ml fluid containing 25 mg of melatonin. The delivery of the fluid is to be performed via an enema. The subjects will be asked to defecate, if possible in the morning, prior to the administration of melatonin.

Study session 3: Intravesical administration

The melatonin/dimethyl sulfoxide (DMSO) aqueous solution will be administered intravesically, followed by plasma samples over the following 24 hours. The melatonin used in the study will be applied intravesically through a catheter at a dose of 25 mg in 50 ml of a solution of 50% (w/w) DMSO in water, the solution containing melatonin at a concentration of 0.5 mg/ml. The subjects will be asked not to consume fluids three hours prior to the start of the study day, and will be asked to void their bladder prior to administration of melatonin.

Study session 4: Vaginal administration

The vaginal suppository containing melatonin will be administered vaginally, followed by plasma samples over the following 24 hours. The melatonin used in the study will be applied at a dose of 25 mg in a suppository (Witepsol S58) vaginally, by the participant themselves.

Study session 5: Transdermal administration

The melatonin will be administered topically as 1 g of a 2.5% (w/w) melatonin cream over a skin area of 20 x 20 cm (400 cm²), followed by plasma samples over the following 48 hours. The dose of melatonin used in the study will thus be 25 mg. The participants will be asked to refrain from using any other creams or lotions one day prior to the study session, and for the following 48 hours.

Outcomes

The outcomes are identical for four of study sessions of the trial (intravenous, rectal, intravesical, and vaginal). The transdermal study session will have a follow-up of 48 hours rather than 24 hours. These differences are outlined below.

Primary outcome

Plasma concentration of melatonin at baseline, 0 min, 10 min, 20 min, 30 min, 40 min, 50 min, 1 hour, 2 hours, 3 hours, 4 hours, 6 hours, 8 hours, and 24 hours. Blood samples are drawn from a peripheral venous catheter within the first 8 hours, and the 24-hour samples will be taken as a single venipuncture. Each blood sample will have a volume of 6 ml, totaling 84 ml for each of the four first study sessions. For the blood samples drawn from a peripheral venous catheter, 4 ml of blood

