
will be drawn as “waste”, to ensure that the following 6 ml consist of undiluted blood, totaling another 52 ml of blood. In total, the subjects will have 136 ml of blood samples each study session.

For the transdermal study session, blood samples are drawn at baseline, 0 min, 30 min, 1 hour, 2 hours, 4 hours, 6 hours, 8 hours, 10 hours, 12 hours, 16 hours, 24 hours and 48 hours. Intervals are based on data from previous pharmacokinetic studies of transdermal melatonin [23]. Blood samples are drawn from a peripheral venous catheter within the first 16 hours, and the 24- and 48-hour samples will be sampled through a single venipuncture each. Each plasma sample will have a total volume of 6 ml, totaling 78 ml for the transdermal study session. For the blood samples drawn from a peripheral venous catheter, 4 ml of blood will be drawn as “waste”, to ensure that the following 6 ml consist of undiluted blood, totaling another 44 mL of blood. In total, the subjects will have 122 ml of blood drawn samples for the transdermal study session.

Plasma samples will be kept in a locked freezer (with a temperature-alarm) at the Department of Surgery, Herlev Hospital. The plasma concentration will be assessed by radioimmunoassay (RIA)-technique at Gastrolab, Herlev Hospital. RIA-technique is a validated method of determining melatonin in plasma that has been used for years [28]. A bio-bank will be created, containing solely the plasma samples from this study (see Data Management for further details). In the case report forms (CRF), the collection time of each sample will be noted. The plasma concentrations will be delivered to the investigator digitally from the laboratory, and will afterwards be noted in the through double entry CRF, by independently two investigators.

Secondary outcomes

Sedative effects and other adverse effects

A Karolinska sleepiness scale (KSS)-score will be performed at baseline and once every hour for 8 hours, as well as at 24 hours, and noted in the CRF. For the transdermal study session, the score will

be performed at every hour on the first day until 16 hours, as well as at 24 and 48 hours. The KSS is frequently used to evaluate subjective sleepiness. The scale has been validated against performance and EEG-variables [29].

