The setting is identical for study sessions one, two, three and four (intravenous, rectal, intravesical and vaginal) of the study. The subjects will be greeted and placed in a room where both the research assistant and the subject can sit comfortably without disturbance. Here the subject will be fitted with a single intravenous access and the baseline sample will be drawn. For the intravenous session, the subject will have two intravenous lines established (one in each arm). Afterwards, the subject will be led to a nearby lockable disturbance free room with a bed for the intravenous, rectal, intravesical, and vaginal study sessions. For the intravenous session, the melatonin will be administered in the arm contralateral to that from which the blood samples are drawn, after which the intravenous access will be removed. The administration of intravenous, rectal and intravesical melatonin will be performed by an investigator. The subjects will administer the vaginal melatonin themselves. Afterwards the subject will be led back to the first room, for the

remainder of the study day for continuous blood sampling and be evaluation of sedative effects and other adverse effects. After the blood sample at 8 hours, the intravenous access will be removed (later for the transdermal study, as described below). The subjects will be offered to have a chaperone present for the rectal, intravesical and vaginal administration of melatonin.

For the transdermal administration, the subjects will be greeted and placed in a room where both the research assistant and the subject can sit comfortably without disturbance. The subject will be fitted with a single intravenous access. The baseline blood sample will be drawn, and the melatonin cream will be administered over a 20 x 20 cm skin area of the thorax by the investigator and subject as described above. The subjects will be evaluated for sedative and other adverse effects. The subjects will remain in this room for the remainder of the study day. After the blood sample at 16 hours, the intravenous access will be removed. The subjects will be offered to have a chaperone present for the administration of the melatonin cream.

Following each study day, a blood sample will be drawn at 24 hours (and 48 hours for the transdermal study session) after administration of melatonin with a regular blood sampling kit. The setting for the 24- and 48-hour blood sample is identical for all five sessions of the study.

Statistics

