The number of patients needed for this study is not based on a power calculation. We have decided that 8 subjects are needed to collect information of how the plasma concentrations develop over time. Because of the risk of dropouts, we have chosen to include a total of 10 subjects.

Data will be presented as either mean (SD) or median (IQR), unless stated otherwise.

Data will be analyzed using IBM SPSS Statistics for Windows version 22.0 (IBM Corp., Armonk, NY, USA) and Graph Pad Prism version 7.0 (Graph Pad Software Inc., La Jolla, CA, USA).

Time to maximal concentrations (t_{\max}) and maximal plasma concentrations (C_{\max}) will be assessed directly at the relevant time points. The pharmacokinetic variables: absorption constant (k_a), absorption half-life ($t_{1/2}$ absorption), elimination rate constant (k_e) and elimination half-life ($t_{1/2}$ elimination) will be estimated by “the method of residuals” [57]. Areas-under-the-curve (AUC) of plasma concentrations will be calculated by applying the trapezoidal rule [58]. $AUC_{0-\infty}$ will be estimated as $AUC_{0-8 \text{ hours}} + (C_{8 \text{ hours}}/k_e)$. Bioavailability (f) will be calculated as follows:

$$f = 100 \times \frac{AUC_{0-\infty} (\text{rectal, intravesical, vaginal or transdermal}) \times D_{iv}}{AUC_{0-\infty} (iv) \times D_{\text{rectal, intravesical, vaginal or transdermal}}}$$
 where D represents the dose

administered.

Data monitoring and management

This study will be conducted in compliance with the protocol, the ICH-GCP guidelines and the applicable regulatory requirements. The standard procedures for quality control and quality assurance are followed in compliance with the ICH-GCP guidelines, and investigator/sponsor allows direct access to data/documents for monitoring, auditing, and inspection from both the Danish Medicines Agency (Lægemiddelstyrelsen) and the Good Clinical Practice (GCP)-unit. The GCP-unit will monitor the study. Data will be stored electronically on a secure server until 10 years

after the end of the study, after which all person-sensitive data are deleted. Blood samples will be destroyed after analysis, at a maximum of one year after sampling. A biobank will be created, solely containing these blood samples. Until analysis, the blood samples are kept in a locked freezer at -80°C (with a temperature-alarm) in a locked room at Gastroenheden D, Herlev Hospital. The blood samples will be analyzed with the RIA-technique at Gaslab, Herlev Hospital.

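### Transdermal bioavailability rests on an area measured only to 8 h, although that session is sampled to 48 h; it is accurate only if concentrations already fall mono-exponentially at the ke used by 8 h

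*Combined protocol and SAP*

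**What the plan says.** Statistics section: the only rule for the total area is "AUC_{0-\infty}$ will be estimated as $AUC_{0-8 \text{ hours}} + (C_{8 \text{ hours}}/k_e". The formula for f directly below it lists the transdermal route among those that use this area. ka and ke are to come from "the method of residuals", without saying which samples define the terminal phase. On the area itself the plan says "Areas-under-the-curve (AUC) of plasma concentrations will be calculated by applying the trapezoidal rule [58", without saying linear or logarithmic. It does not mention subtracting the baseline sample.

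Outcomes: "The transdermal study session will have a follow-up of 48 hours rather than 24 hours".

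Primary outcome, transdermal: "For the transdermal study session, blood samples are drawn at baseline, 0 min, 30 min, 1 hour, 2 hours, 4 hours", continuing through "8 hours, 10 hours, 12 hours, 16 hours, 24 hours and 48 hours". The other four sessions end with "4 hours, 6 hours, 8 hours, and 24 hours".

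Setting, transdermal: "After the blood sample at 16 hours, the intravenous access will be removed".

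**The concern.** An 8 h end point suits the four sessions that are sampled densely to 8 h and then only once more. The transdermal session has its own schedule, which the plan bases on earlier transdermal studies, but the area rule was not adapted to it. Five of its 13 samples fall after 8 h and cannot contribute measured area. Everything beyond 8 h is replaced by one extrapolated term, C8/ke.

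That term is right only if nothing but mono-exponential decline at the chosen ke is left by 8 h. If the skin is still delivering drug in another pattern, f is wrong although the data to correct it have been collected. The background text states that transdermal bioavailability has not been studied before, so this is one of the figures readers will look for.

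**Working it through.** **No figure to reproduce.** The plan states no area, f, ke, half-life or quantification limit (LOQ). The stated blood volume confirms the schedule: 13 × 6 ml + 11 × 4 ml = 122 ml.

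**When the rule is exact.** C8/ke equals the area after 8 h if concentration from 8 h on is C8·exp(−ke·(t − 8)). If ke is the true elimination constant, mass balance gives

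(AUC0-8 + C8/ke) / true AUC = share of the absorbed drug that has entered by 8 h.

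For first-order absorption with half-life h this is 1 − 2^(−8/h): 0.94 at 2 h, 0.75 at 4 h, 0.50 at 8 h and 0.37 at 12 h. For constant input over T hours it is 8/T: 0.67 at 12 h, 0.50 at 16 h and 0.33 at 24 h.

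**One case by hand** (assumed: elimination half-life 0.75 h, absorption half-life 8 h, absorbed dose/volume = 1).
- ke = 0.693/0.75 = 0.924 per h, so true AUC = 1/0.924 = 1.082. The absorption rate is 0.693/8 = 0.0866 per h.
- C8 = 0.0866/(0.924 − 0.0866) × (0.5 − 0.0006) = 0.0516.
- 55.2% of the area lies after 8 h, so AUC0-8 is 44.8% of the total.
- With the elimination constant, C8/ke = 0.0516/0.924 = 0.056, or 5.2% of the total. The rule returns 44.8 + 5.2 = 50%.
- With the curve's own terminal slope (here the absorption rate), C8/slope = 0.0516/0.0866 = 0.596, or 55.1%. The rule returns 99.9%.

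The same rule on the same curve is therefore almost right or half right, depending on what is called ke.

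**Range under assumptions.** One-compartment model at the planned transdermal times; elimination half-life 0.5, 0.75, 1.0 or 1.5 h; LOQ 1% or 5% of Cmax; linear trapezoid; no noise. "Delayed" means three-stage transit input. The two 8 h columns assume no endogenous melatonin. The own slope is fitted to the last three quantifiable post-peak samples. The last column is the rule proposed under the fix, with a constant endogenous level of 0, 2 or 5% of Cmax and these example cut-offs: last sample at least twice baseline, extrapolation at most 20% of the total, and area ended at 24 h if concentration there is at least half of Cmax.

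| Input | 8 h rule, own slope | 8 h rule, elimination ke | Proposed rule |
|---|---|---|---|
| First-order, half-life 2/4/8/12 h | 97-100% | 92-93/74/49/37% | 98-100% |
| Delayed, mean 6/9/12 h | 92-94 / 75-94 / 72-78% | not needed for the point | 98-104% |
| Constant, 12/16/24 h | no usable slope in 24 of 24 cases | about 67/50/33% (8/T) | 86-99%, partial area only |

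**Endogenous melatonin.** With an unsubtracted constant level of 2% of Cmax, the 8 h rule with the session's own slope ranges from 75% to several hundred percent of the true area. The late samples sit on the flat endogenous level, the fitted ke becomes too small, and C8/ke becomes too large.

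**The case against.** The method of residuals reads ka and ke from one absorption curve, so the natural reading is that each session supplies its own ke. On that reading, with plain first-order absorption and no endogenous signal, the rule returns 97-100% and the 8 h cut-off hardly matters. This stands. The larger losses need delayed or prolonged input, and the documents give no input profile for this cream. The 8 h cut-off might also have been meant to keep night-time endogenous melatonin out of the area, but the plan gives no such reason, no clock times and no baseline correction.

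A reader might infer that transdermal f will be halved or worse. That needs an elimination ke such as the intravenous value, which the plan does not state, together with an absorption half-life of about 8 h or more. A reader might also infer that f will be too low. The direction is not fixed, because endogenous melatonin can push it upward. Nor are the five late samples discarded: they remain primary-outcome concentrations and can inform Cmax, tmax and ke.

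It is also true that f is descriptive, from 8 to 10 women with no hypothesis test, and can be recomputed later. What would be lost is that the rule was chosen before the data were seen.

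**Conclusion.** The mismatch is certain: one 8 h rule, applied to a route sampled to 48 h, with no transdermal exception anywhere in the plan. Its effect on f is conditional, and the documents settle neither size nor direction. With the session's own slope and no endogenous signal, the rule runs from nearly exact (first-order absorption) to 72-94% of the true area (delayed input, mean 6-12 h), and it yields no total area for constant input of 12-24 h. These ranges rest on the assumed one-compartment model, half-lives and LOQ in the working. The proposed rule also gives no full total area for prolonged constant input; its gain there is a usable, flagged partial area. The point should be fixed, but its reach is limited to a derived figure and the primary concentrations are untouched.

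**What to change.** In the Statistics section, for the transdermal session, replace the 8 h rule with AUC0-tlast + Clast/λz:

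- tlast is the last quantifiable sample above baseline, up to 48 h.
- The trapezoid is linear while concentrations rise and logarithmic while they fall.
- λz is the log-linear slope of that session's own last three post-peak samples up to tlast.
- If there is no valid slope, or the extrapolated part is large, report AUC0-tlast and the f based on it, flagged as not extrapolated.
- If concentration is still near its peak at 24 h, end the area at 24 h and flag it in the same way.

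Fix the exact cut-offs before concentrations are seen; those in the working are examples. Subtract each session's own baseline sample in all five sessions, including intravenous, so that both areas in f are baseline-corrected. Keep the 8 h end point for the other four routes, which have no samples between 8 and 24 h, and state that ke comes from that session's own declining samples. Show the unsubtracted result and the plan's 8 h rule for the transdermal route as sensitivity analyses.

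Cost: a few sentences, with no new samples or assays. Downsides: a single baseline value removes only a constant endogenous level. The transdermal day is paid for 17 hours, so with an assumed morning start the 16 h sample falls at night, and an endogenous rise could affect it. For prolonged constant input the result is only a partial area, about 86-99% of the true one.
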